3. OBJECTIVES, ESTIMANDS, AND ENDPOINTS

3.1. Efficacy Objectives, Estimands, and Endpoints

Objectives	Endpoints	Estimands
Primary:	Primary:	Primary:
To demonstrate superior efficacy of treatment with fordadistrogene movaparvovec as compared to placebo based on change from Baseline in the North Star Ambulatory Assessment (NSAA).	Change from Baseline at Week 52 in the NSAA total score.	Primary Estimand: Population: Boys with a genetic diagnosis of DMD who are ambulatory and age ≥ 4 to < 8 years; Variable: Change from Baseline at Week 52 in the NSAA total score; Death or loss of ambulation are identified as potential intercurrent events. Population-level summary: difference in mean changes from Baseline at Week 52 in the NSAA total score between fordadistrogene movaparvovec and placebo.
Secondary:	Secondary:	Secondary:
To quantify the mini-dystrophin expression level in the muscle of participants treated with fordadistrogene movaparvovec.	Change from Baseline in percent normal mini-dystrophin expression level in biceps brachii muscle biopsies at Day 360 using an LCMS assay.	Secondary Estimands: Population: Boys with a genetic diagnosis of DMD who are ambulatory and age ≥ 4 to < 8 years;
To characterize the distribution of mini-dystrophin expression in the muscle of participants treated with fordadistrogene movaparvovec.	Change from Baseline in percent of muscle fibers expressing mini-dystrophin in biceps brachii muscle biopsies at Day 360 as assessed by immunofluorescence.	Variable: Each secondary endpoint;

Objectives	Endpoints	Estimands
To characterize the change in serum creatine kinase (CK) concentration in participants treated with fordadistrogene movaparvovec as compared to placebo.	Change from Baseline at Week 52 in serum CK concentration.	Death or loss of ambulation are identified as potential intercurrent events. Population-level summary: difference in means between fordadistrogene movaparvovec and placebo for each secondary endpoint.
To characterize the skills gained, based on the individual items of the NSAA, in participants treated with fordadistrogene movaparvovec as compared to placebo.	Number of skills gained at Week 52 based on the individual items of the NSAA.	

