5.1. Inclusion Criteria

Participants are eligible to be included in the study only if all of the following criteria apply:

1. Male participants who are ≥ 4 and < 8 years of age at Screening (Visit 1).
2. Confirmed diagnosis of DMD by prior genetic testing demonstrating the presence of a mutation in the dystrophin gene consistent with DMD at Screening (Visit 1). If the

Investigator determines that the results are inconclusive, a repeat genetic testing will be allowed through the central laboratory at Screening (Visit 1).

3. Receipt of a stable daily dose of glucocorticoids (≥ 0.5 mg/kg/day prednisone, prednisolone, or ≥ 0.75 mg/kg/day deflazacort) for at least 3 months prior to Screening (Visit 1) and during the period between Screening (Visit 1) and Day 1 (Visit 3). In order to comply with protocol procedures, there should also be a reasonable expectation that this daily dose of glucocorticoids will remain stable for the first 2 years of the study. A stable dose is defined as one in which any change is ≤ 0.2 mg/kg (See [Section 6.5.1](#) for detailed requirements).
4. A NSAA total score >16 and <30 at Screening (Visit 1).
5. Ambulatory, defined as being able to walk 10 meters unassisted, at Screening (Visit 1).
6. Participants/legally acceptable representatives who are willing and able to comply with all scheduled visits, treatment plan, laboratory tests, lifestyle considerations, and other study procedures including, potentially, open muscle biopsies under general anesthesia and cardiac MRI under general anesthesia.
7. Participants/legally acceptable representatives who are capable of giving assent/signed informed consent as described in [Appendix 1](#), which includes compliance with the requirements and restrictions listed in the assent/informed consent document (ICD) and in this protocol.
8. Participants/legally acceptable representatives who are willing to protect the integrity of the study data by not actively seeking sensitive clinical data (eg, CK, ALT, AST, NAb to AAV9) through independent laboratory tests and by not sharing trial experiences with other participants or publicly (eg, through social media).

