9.1. Estimands and Statistical Hypotheses

For the primary endpoint, the null hypothesis is that there is no difference between fordadistrogene movaparvovec and placebo with respect to mean change from Baseline at Week 52 in the NSAA total score. The alternative hypothesis is that fordadistrogene movaparvovec is different from placebo with respect to mean change from Baseline at Week 52 in the NSAA total score.

The experiment-wise Type I error of $\alpha=0.05$ (two-sided) will be controlled using gatekeeping and fixed-sequence procedures for the primary and select secondary endpoints listed below. The hypotheses for the secondary endpoints are similar to those for the primary endpoint.

1. Change from Baseline at Week 52 in the 10 meter run/walk velocity.
2. Change from Baseline at Week 52 in the rise from floor velocity.
3. Number of skills either improved or maintained at Week 52 based on the individual items of the NSAA.
4. Number of skills gained at Week 52 based on the individual items of the NSAA.

If the null hypothesis for the primary endpoint is rejected, statistical testing proceeds to the hypotheses for the secondary endpoints; otherwise, formal statistical testing in the sense of controlling the experiment-wise Type I error stops and nominal p-values for secondary endpoints will be reported and interpreted accordingly.

The secondary endpoints will be tested in the order specified above. To maintain the study-wise type 1 error rate, the p-value boundary for these secondary endpoint analyses will be the same as the primary analysis as detailed in the Interim Analysis SAP.. If the null hypothesis for the first endpoint in the sequence is rejected, statistical testing moves to the next endpoint in the sequence. Statistical testing proceeds to subsequent endpoints in the sequence only if the null hypothesis for the previous endpoint is rejected. If a null hypothesis in the sequence is not rejected, formal statistical testing in the sense of controlling the experiment-wise Type I error is stopped for all endpoints later in the sequence and nominal p-values will be reported and interpreted accordingly.

The null hypothesis for the primary and secondary endpoints will be tested at Week 52 using the parameter and variance estimates from the MMRM model or the generalized mixed model described in [Section 9.4.1](#).

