9.4.1. Efficacy Analyses

Endpoint	Statistical Analysis Methods
Primary	
Inferential testing for the primary analysis for the primary endpoint will be performed at $\alpha=0.05$ (two-sided).
 
Baseline NSAA total score is defined as the last non-missing NSAA total score collected prior to Year 1 IP administration.
 
Primary analysis: Change from Baseline at Week 52 in the NSAA total score will be analyzed using a mixed model repeated measures approach including visits through Week 52 where NSAA is assessed. The analysis will be based on the FAS (Regardless of adherence to glucocorticoid regimen) and missing data will not be explicitly imputed. The model will include fixed effects for treatment (class variable), visit (class variable), treatment by visit interaction, Baseline NSAA total score (continuous variable), Screening age (continuous variable), Baseline NSAA total score by visit interaction, and Screening age by visit interaction with an unstructured covariance matrix to describe the correlation among different visits from the same participant. Alternative covariance structures to address any issues with model convergence will be specified in the SAP. To test the null hypothesis, estimates at Week 52 of the mean changes from Baseline and 95% confidence intervals along with the mean treatment group difference, two-sided p-value, and two-sided 95% confidence interval for the mean difference will be provided.
 
Sensitivity analyses to assess the effect of missing data will be described in the SAP.

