Secondary	
Inferential testing of the secondary endpoints will be performed as described in Section 9.1.
 
Baseline is defined as the last non-missing assessment collected prior to Year 1 IP administration.
 
The following endpoints will be analyzed using an analysis of covariance model including model terms for treatment group, Baseline (continuous variable), and Screening age (continuous variable).
 
• Change from Baseline in percent normal mini-dystrophin expression level in biceps brachii muscle biopsies at Day 360 using LC-MS assay.• Change from Baseline in percent of muscle fibers expressing mini-dystrophin in biceps brachii muscle biopsies at Day 360 as assessed by immunofluorescence. 
Change from Baseline at Week 52 in serum CK concentration will be analyzed using a mixed model repeated measures approach and a log transformation. The model fixed effects will be similar to those in the primary endpoint analysis and visits through Week 52 where serum CK concentration is assessed will be included.

Endpoint	Statistical Analysis Methods
	
The below two endpoints will be analyzed using a generalized mixed model assuming a binomial distribution and a logit link. The model terms will include treatment and Screening age (continuous variable).
 
Number of skills gained at Week 52 based on the individual items of the NSAA. For each individual item, a gained skill is defined as a score of 0 at Baseline and a score of 1 or 2 at Week 52.Number of skills either improved or maintained at Week 52 compared to Baseline based on the individual items of the NSAA. For each individual item, an improved or maintained skill is defined as a score of 0 at Baseline and a score of 1 or 2 at Week 52, a score of 1 at Baseline and a score of 2 at Week 52, a score of 1 at Baseline and a score of 1 at Week 52, or a score of 2 at Baseline and a score of 2 at Week 52. 
The following endpoints will be analyzed using a similar mixed model repeated measures approach as used for the primary analysis.
 
Change from Baseline at Week 52 in the 10 meter run/walk velocity;Change from Baseline at Week 52 in the rise from floor velocity;Change from Baseline at Week 52 in the Modified PODCI: Transfer and Basic Mobility Core Scale (Pediatric Parent);Change from Baseline at Week 52 in the Modified PODCI: Sports and Physical Functioning Core Scale (Pediatric Parent).

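### The models for the two alpha-controlled NSAA skills endpoints leave out Baseline NSAA and so give up some power, mainly for skills improved or maintained

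*Protocol*

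**What the plan says.** Protocol section 9.1 controls the two-sided 0.05 error rate through the primary endpoint and then four ordered secondary endpoints. The third is "Number of skills either improved or maintained at Week 52 based on the individual items of the NSAA"; the fourth is the number of skills gained.

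Section 9.4.1 describes their analysis: "The below two endpoints will be analyzed using a generalized mixed model assuming a binomial distribution and a logit link". It then lists the terms: "The model terms will include treatment and Screening age (continuous variable". It states neither the binomial denominator nor the random effect.

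The definitions in the same section start from the Baseline item score. For one endpoint, "a gained skill is defined as a score of 0 at Baseline and a score of 1 or 2 at Week 52". For the other, "an improved or maintained skill is defined as a score of 0 at Baseline and a score of 1 or 2 at Week 52", or a 1 that stays 1 or becomes 2, or a 2 that stays 2. An item at 0 on both occasions therefore counts as a failure.

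The other models treat Baseline differently. The primary model contains "Baseline NSAA total score (continuous variable), Screening age (continuous variable), Baseline NSAA total score by visit interaction". The biopsy ANCOVA names Baseline. CK, both velocities and both PODCI scales follow the primary model.

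**The concern.** The number of skills a boy can gain is capped by the number of items at 0 when he starts, and his improved-or-maintained count falls by one for each such item that stays at 0. Baseline function therefore explains part of the between-boy spread in both counts. Randomization is stratified by Screening age only, and age is also the only covariate kept. Variation that an already collected measurement could absorb is left in the error term of two confirmatory tests, in a trial with about 96 evaluable boys split 2:1. What is at stake is power at steps three and four of the sequence.

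**Working it through.** **Inputs from the protocol.** 99 participants randomized 2:1 with 3 dropouts, so 64 and 32 evaluable; difference 3.0; SD 3.5 (section 9.2). The NSAA has 17 items scored 0, 1 or 2 (section 8.1.1). Entry requires "A NSAA total score >16 and <30 at Screening (Visit 1") (section 5.1), that is, totals of 17 to 29.

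**The plan's own figure.** SE = 3.5 × √(1/64 + 1/32) = 0.758. Then 3.0/0.758 = 3.96, and 3.96 − 1.96 = 2.00, so power is 97.7%, against 98% stated. With gamma(−1) spending and looks at 30, 60 and 96, cumulative crossing probabilities are 36.7%, 78.8% and 97.0%, against 38%, 78% and 97% stated. The protocol gives no power for the skills endpoints.

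**Structural check.** A boy with z items at 0 can score at most 2 × (17 − z). A total T therefore allows at most 17 − ⌈T/2⌉ zeros:
- T = 17: 17 − 9 = 8 zeros
- T = 29: 17 − 15 = 2 zeros

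A boy whose items do not change at all has an improved-or-maintained count of 17 − z. That is 9 of 17 with eight zeros and 15 of 17 with two, a difference due to Baseline alone.

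**Simulation.** 300 trials per scenario, 64 versus 32 boys, 17 ordinal items, Baseline totals 17 to 29. The model was a binomial logit model with a participant random intercept, fitted with and without Baseline NSAA total score. The item parameters and the random intercept are assumptions. Power is for each test alone at nominal two-sided 0.05. The simulated NSAA difference was 2.83 to 2.89, and the SD of change was varied around 3.5.

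| Endpoint (denominator) | SD of change | SE without → with Baseline | SE ratio | Power without → with |
|---|---|---|---|---|
| Improved or maintained (17) | 2.89 | 0.196 → 0.162 | 0.827 | 95.3% → 100% |
| | 3.45 | 0.224 → 0.196 | 0.875 | 91.0% → 96.0% |
| | 4.09 | 0.258 → 0.234 | 0.907 | 79.3% → 86.0% |
| Gained (items at 0) | 2.89 | 0.322 → 0.302 | 0.938 | 82.3% → 87.7% |
| | 3.45 | 0.362 → 0.345 | 0.953 | 73.7% → 79.7% |
| | 4.09 | 0.412 → 0.397 | 0.964 | 63.0% → 66.7% |
| Gained (17) | 2.89 | 0.209 → 0.207 | 0.990 | 66.7% → 66.3% |
| | 3.45 | 0.215 → 0.206 | 0.958 | 60.3% → 61.3% |
| | 4.09 | 0.223 → 0.209 | 0.937 | 48.3% → 55.0% |

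In the middle scenario Baseline total correlated −0.40 with skills gained and +0.44 with improved or maintained. Screening age correlated −0.13 and −0.18.

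**Type I error without Baseline**, no effect simulated: 4.0% for improved or maintained, and 5.0% or 6.7% for gained (items at 0, or 17). The Monte Carlo standard error is √(0.05 × 0.95/300) = 1.3 points, so all three are compatible with 5%.

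**The case against.** The strongest reply is that this is a preference for efficiency and not an error. That is right about validity. A reader might infer that a chance imbalance in Baseline zeros biases the treatment effect. It does not: under randomization such imbalance is random error that the unadjusted SE already covers, and simulated type I error was near nominal.

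A reader might also expect the largest loss for skills gained, because its ceiling depends most visibly on Baseline. The simulation does not bear this out. If the denominator is the number of items at 0, the model already conditions on much of the Baseline information. If it is 17, the gain at the planned SD is about one point of power. The denominator is unstated, so the documents do not settle which case applies.

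Odds ratios are non-collapsible, so SEs from models with different covariates are not strictly like for like, and power is the fairer measure. The caution stands in principle. Here the log-odds estimate for improved or maintained barely moved (0.731 without Baseline, 0.727 with).

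A further inference would be that the model contradicts the secondary estimand, "Population-level summary: difference in means between fordadistrogene movaparvovec and placebo for each secondary endpoint", because a logit model yields odds ratios. The documents do not go that far. That summary is one generic line for all secondary endpoints, and a difference in mean counts can be derived from a logit model. This is a separate reporting matter.

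Finally, section 9 lets the SAP modify the protocol, and only the protocol was available here. That mitigates in part. Section 9.4.1 explicitly defers covariance structures and missing-data sensitivity analyses to the SAP, but it fixes these covariates itself. The two tests are also reached only after the primary endpoint and both velocities succeed.

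**Conclusion.** The point holds as a modest loss of efficiency. The protocol fixes treatment and Screening age as the only terms for two confirmatory endpoints that are defined from Baseline item scores, while adjusting for Baseline in every other primary and secondary model. At about the planned difference and SD, adding Baseline NSAA total score is worth about 12% in SE (9% to 17% across the SDs tried) and about five points of power for improved or maintained. For skills gained it is worth 1% to 6% in SE and between one and six points of power at the planned SD, depending on the denominator.

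The direction follows from the definitions. The sizes rest on assumed item parameters, a participant random intercept, 300 trials per scenario and nominal alpha. The 17 to 29 range is a Screening criterion, and Baseline, the last pre-dose assessment, may differ somewhat. That Baseline matters more than age is a result of the assumed item model and is not stated in the protocol.

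**What to change.** Before unblinding, change the sentence on model terms in section 9.4.1, and its counterpart in the SAP, along these lines: *Both skills models will contain treatment, Baseline NSAA total score and Screening age, the last two as continuous variables.* In the same place, state the binomial denominator for each endpoint (all 17 items, or the items scored 0 at Baseline).

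The cost is a sentence or two, and the NSAA is already collected at Screening and Baseline. The one small drawback is that the odds ratio becomes conditional on Baseline, so its value is not directly comparable with an unadjusted one.

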9.4.2. Safety Analyses

All safety analyses will be performed on the safety population.

Statistical Analysis Methods

Descriptive summaries through Week 52 will be provided by treatment group for participants in the Safety (through Week 52) population for the following:
 
• Incidence, severity, and causal relationship of TEAEs (AEs and SAEs);• Incidence of abnormal laboratory findings and magnitude of change;• Abnormal and clinically relevant changes in:
• Physical exam;• Neurological exam;• Weight;• Vital signs;• ECG;• Echocardiogram;• Cardiac MRI;• CBCL.

Descriptive summaries relative to pre-fordadistrogene movaparvovec baseline through Year 2 Week 52 for participants in the Safety (Cohort 2 delayed treatment) population will be provided for the above safety parameters.

Descriptive summaries relative to pre-fordadistrogene movaparvovec baseline through 5 years post fordadistrogene movaparvovec administration for participants in the Safety (long-term) population will be provided for the above safety parameters for combined Cohorts 1 and 2.

9.4.2.1. Electrocardiogram Analyses

Changes from Baseline through Week 52 for the ECG parameters QT interval, heart rate, QTc interval, PR interval, and QRS complex will be summarized by treatment and time. Changes in the above ECG parameters from pre-fordadistrogene movaparvovec baseline to Year 2 Week 52 for participants in Cohort 2 and at 1, 2, 3, 4 and 5 years post fordadistrogene movaparvovec administration will be summarized.

9.5. Interim Analyses

There are 2 options for interim analyses, both of which are designed to provide data to support an earlier regulatory submission for BLA/MAA based on the primary endpoint of change from Baseline at Week 52 in the NSAA total score. The objective of each interim analysis is to demonstrate a statistically significant effect of fordadistrogene movaparvovec on the primary endpoint of change from Baseline at Week 52 in the NSAA total score compared to placebo. Additionally, an assessment of futility (non-binding) based on the primary endpoint will be made at each interim analysis, if performed.

The first interim analysis may be performed when approximately 30 participants in the FAS have completed visits through Week 52, and the second interim may be performed when

approximately 60 participants in the FAS have completed visits through Week 52. The decision to conduct either interim analysis will be based on regulatory feedback, study recruitment rates and emerging data from other studies in the program. The objectives, estimands, endpoints, and analysis method for each interim analysis are identical to the primary analysis ([Section 9.4.1](#)). If either interim analysis is performed, a group sequential approach will be applied to the efficacy analyses to control Type I error across the interim analysis/analyses and the primary analysis. Specifically, a gamma family alpha-spending function with gamma parameter -1 will be used. Additionally, an assessment of futility (non-binding) based on the primary endpoint will be made at each interim analysis, if performed, using a gamma family spending function with gamma parameter -4.

Before any interim analysis is implemented, the details of the objectives, decision criteria (based on the actual number of participants and the number of looks), dissemination plan, method of maintaining the study blind, and analysis details will be recorded in the appropriate study documents. The interim analysis/analyses will be performed by an independent team of statisticians and programmers, and the results will be unblinded only to the E-DMC and/or a limited number of individuals within the Sponsor organization who are not involved in the conduct or further analysis of the ongoing study. These unblinded individuals from the Sponsor organization will be responsible for reviewing the results from the interim analyses and making a recommendation on pursuing a regulatory submission based on the interim analysis results.

The timing of public disclosure of the results of either interim analysis will be at the discretion of the Sponsor. If disclosure of interim analysis results prior to completion of the C3391003 trial is believed to have the potential to interfere with study completion, the Sponsor may choose to delay disclosure of the interim analysis until the trial has completed.

Irrespective of whether an interim analysis has been conducted, the primary analysis will occur after at least 90 FAS participants complete Day 360 (Visit 19) or discontinue from the study prior to Week 52, if they had received Year 1 IP at least one year prior to the data cutoff. . After the database has been released for the primary analysis, the study may become fully unblinded. If either an interim analysis is performed and the objectives are not met, the nominal type I error for the primary analysis will be adjusted accordingly. If either interim analysis is performed and the objective is met, the primary analysis at Week 52 will primarily be used to provide a more precise estimate of the treatment difference for the primary endpoint.

Additional analyses may be performed after the primary analysis, as needed, per regulatory requirements or in support of publications.

